For patients included during these 15 months, we will collect data at baseline, directly after the end of the program and 6 and 12 months after the start of intervention. In this stepped wedge study, we have set our measurement periods at time intervals of three months, resulting in a total inclusion duration of 15 months, an implementation period of 3 months and a follow-up of 12 months (thus clinical study duration 30 months in total). At the start of the study, all clusters start together in the control group, where none of the practices work according to the Coach2Move strategy and provide usual care. At different time points the clusters will cross-over to the intervention condition. The time points at which the different practices transition to Coach2Move are determined at random. By the end of the trial, all practices will have implemented Coach2Move.

The Implementation and Wash-out period consists of 3 months in which the therapists retrieve a 2-day education in Coach2Move and in which 3 peer assessment meetings take place. During this period, no measurements are carried out to give the therapists the opportunity to gain experience with Coach2Move before the measurements commence in the intervention period. This has no direct consequences for the participants.

All data will be collected by researchers from Radboudumc. Data sampled at baseline relevant for clinical decision-making will be communicated to the PT(G), to avoid load on the patient.

Figure 1. Depiction of proposed stepped wedge, cluster randomised design.

	3 months	6 months	9 months	12 months	15 months	18 months
Group 1 (Practices 1,2,3,4)	Control	Imp + WO	Intervention	Intervention	Intervention	Intervention
Group 2 (Practices 5,6,7,8)	Control	Control	Imp + WO	Intervention	Intervention	Intervention
Group 3 (Practices 9,10,11,12)	Control	Control	Control	Imp+ WO	Intervention	Intervention
Group 4 (Practices 13,14,15,16)	Control	Control	Control	Control	Imp+ WO	Intervention

Abbreviations: Imp +WO = Implementation and wash-out period.

A mixed methods process evaluation is designed to investigate the processes through which the Coach2Move intervention operates on outcomes and how the implementation of the program is achieved in the context of potential organisational and other differences between regions and practices.

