A process analysis has shown that the Coach2Move strategy differed from usual care physiotherapy in almost all physiotherapeutic phases, but the main contrast was defined by a more patient-centered problem analysis and the use of inspiring goals based on shared decision-making, leading to greater adherence and self-management [17]. In a recent international study it was also recognized that patient-centeredness of guidelines should be increased, which resulted in 14 recommendations including patient-centered intervention goals, use of the ICF terminology in problem analysis, adopting a shared decision-making method, and incorporating patient-reported health outcome measures, elements present in the Coach2Move strategy [18]. These key elements are part of the shift from a biomedical to a biopsychosocial perspective on health: defining health as the ability to self-manage and adapt, with not only a focus on illness and interventions, taking into account strengths rather than weaknesses [19]. Although appreciated, this concept requires substantial personal input, of which not everyone is capable of. Although patients are focused on a broad concept of health (especially the elderly), physicians (including PTs) assess health from a more narrow and biomedical standpoint [20]. So the transfer from a biomedical to a biopsychosocial approach seems to be challenging but necessary for successful treatment results [21].

For participants suffering from (mild) dementia, a social chart will be composed consisting of relevant persons and institutions, so participants are able to receive contextual support instead of intrinsic motivations and personal responsibility in the achievement of set goals.

b. Implementation

Initially, all participating practices of physiotherapy treat the subjects by usual care. At some point in time (selected at random) during the Implementation and wash-out period, Coach2Move is introduced through a two-day education program and two peer assessment meetings. In the control period, physiotherapeutic care will take place as usual. To make sure there is no interference in the treatment due to the study, eligible patients are visited by the researcher within 1 week of registration. In that visit, tests and questionnaires are performed which are not included in usual care. During the implementation period, the extensive intake will be carried out under supervision by a researcher of Radboudumc. This is to ensure all necessary tests are performed.

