
Furthermore, it is focussed to guarantee objectivity. Lastly, the PT(G) can be coached and receive feedback to optimize the intake. After the implementation phase, the PT(G) is expected to perform the extensive intake on his or her own without the presence of a researcher. The follow-up measurements are being conducted by the researchers of Radboudumc.

The PT(G) is educated in the Coach2Move strategy in a baseline training of 2 days. The education consists of one physical meeting and a web-based e-learning. This education will focus on:

- Setting priorities in physiotherapy treatment by using an algorithm that emphasizes clinical reasoning.
- Making shared decisions on meaningful treatment goals focused on dissolving barriers exercises, and increasing physical activity.
- Making SMARTI focused goals.
- Focusing on coaching and self- management among patients to increase long-term results.
- Working patient-centered.
- Improving motivational interviewing skills.
- Gaining skills for adequate coordination with other involved formal and informal caregivers.
- Using appropriate measurement instruments in the diagnostic phase but also in the evaluation of the intervention and as feedback instrument for the patient and therapist.

In addition to the e-learning, three meetings will be planned in which peer assessment among participating physiotherapists takes place. Peer assessment is an effective way to improve adherence to new guidelines and approaches. Personal feedback and awareness of professional performance are known to be effective in improving the implementation of new strategies [22]. Moreover, insight into the electronic medical record (EPD) will be provided to researchers to support the clinical reasoning and patient involvement and monitoring process and to stimulate communication with the local care network if available.

c. Comparative arm:

In this study, all participating PT practices will serve as their own control. Initially, all 16 practices will provide their usual PT care. No instructions will be given on treatment content, frequency and/or duration of the treatment episode.

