4. First assessment at the start of the intervention (t0) in which a number of measures will be performed. Questionnaires: LAPAQ, EQ-5D, EFIP, PSC and CIRS-G. In addition, the modified TUG is carried out. This assessment will take approximately 60 minutes and is carried out by one of the researchers during the control period or by one of the participating PT(G)'s during the intervention period.
5. Physiotherapy treatment. In either the experimental or the control group, the physiotherapist determines the number of physiotherapy consults that are needed. This is common in physiotherapy. During the intervention period, the patient and the PT(G) will choose the best fitting intervention profile together.
6. The second assessment (t1) at three months after the start of the intervention: questionnaires: LAPAQ, EQ-5D, EFIP, PSC, GPE and healthcare utilization. Again, the modified TUG is carried out. This assessment will take approximately 45 minutes.
7. The third assessment (t2) at six months after the start of the intervention. Questionnaires: LAPAQ, EQ-5D, EFIP, PSC, GPE, healthcare utilization and adherence. The modified TUG is performed. This assessment will also take approximately 45 minutes and is carried out by the researcher.
8. The fourth assessment (t3) at twelve months after the start of the intervention. Questionnaires: LAPAQ, EQ-5D, EFIP, PSC, GPE, healthcare utilization and adherence. The modified TUG is carried out once again. This assessment will also take approximately 45 minutes and is carried out by the researcher.

A randomised selection of participants is asked to join in focus group meetings to share experiences on Coach2Move. Participation is voluntarily.

All participants will be debriefed after the study by sending an information brochure concerning the most important outcomes and conclusions of the study. In addition, the participating practices for physiotherapy will be sent the same information in flyer format, which they can hang in a visible spot in their practice. Dutch magazines and newspapers will be approached to publish the research outcomes, as has happened during the previous trial of Coach2Move.

Procedure of enrolled therapists in the study:

1. Start with physiotherapeutic care as usual.
2. Electronic medical record (EPD) will be provided to support clinical reasoning and monitoring the process.

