10. ETHICAL CONSIDERATIONS

a. Regulation statement

This study will be conducted according to the principles of the Declaration of Helsinki (version 64, Fortaleza, 2013) and in accordance with the Medical Research Involving Human Subjects Act (WMO).

b. Recruitment and consent

Patients will be recruited in sixteen physiotherapy practices within a 12 month time period. All patients are consecutive patients that meet the inclusion criteria of this study, either referred to physiotherapy by a physician or contacting a physiotherapist by direct access because of mobility problems. Initial information on the study will be given by the secretary of the physiotherapy practice. The secretary will also give an information letter to the potential participants. The investigator of this study and an independent contact person can be approached for questions. The potential participant will get the time he/she needs to think about participation with a maximum of one week. However, it is recommended to commence as soon as possible considering the perceived need for treatment. The researcher will subsequently make an appointment with the participant for the first assessment and will also deal with informed consent. The data of the repeated measurements of the tests on the four assessments (0-, 3-, 6- and 12 months) will be used. Not all patients in this study are

followed for the full duration of this study. From those older adults not eligible based on the in- and exclusion criteria, only clinical data is analysed.

c. Objection by minors or incapacitated subjects

Older adults suffering from mild dementia are eligible to be included in the study as well. Guardians and/or (family) care givers are asked to sign a modified informed consent with strict arrangements when to withdraw the participant. These arrangements are conform Code of Conduct: Incapacitated Elderly.

d. Benefits and risks assessment, group relatedness

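### Sections 4 and 8.c disagree on who measures baseline; under the 8.c split, any systematic assessor difference would bias the baseline-adjusted effect

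*Combined protocol and SAP*

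**What the plan says.** Section 4 (Study design) is general: "All data will be collected by researchers from Radboudumc". It adds that baseline findings useful for care will be passed to the treating physiotherapist, which suggests that someone else obtained them.

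Section 8.c (Study procedures), step 4, is specific. The baseline assessment (T0) covers LAPAQ, EQ-5D, EFIP, PSC, CIRS-G and the modified TUG, and is "carried out by one of the researchers during the control period or by one of the participating PT(G)'s during the intervention period". Two other places agree with this split. Section 7.b says that after implementation "the PT(G) is expected to perform the extensive intake on his or her own without the presence of a researcher", and the list of therapist procedures in section 8.c assigns the intake in the same way.

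For the later visits, section 7.b says: "The follow-up measurements are being conducted by the researchers of Radboudumc".

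Section 9.b compares conditions by multilevel regression, with time as a fixed effect and with age, sex, comorbidity, frailty and baseline physical functioning as covariates. It does not name the instrument for physical functioning. Section 9 describes no assessor variable, agreement check or sensitivity analysis for this point.

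**The concern.** Sites cannot follow sections 4 and 8.c at once. If they follow 8.c, each practice changes its baseline assessor at the same step at which it changes treatment. Suppose researchers and physiotherapists differ systematically in timing, scoring or interviewing. Intervention patients would then look better or worse at baseline than they are, and adjustment would carry that error into the estimated effect. Random disagreement would mainly add noise.

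What is at stake is the adjusted TUG and LAPAQ comparison that decides the trial, and to a lesser extent the QALY difference, where baseline utility enters the outcome directly. An observed baseline difference between conditions could not be attributed to either measurement or case mix.

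**Working it through.** **Inputs from section 6.d.** 16 practices, 5 patients in each of 5 measured periods, ICC 0.10, stated SE 0.21 SD. TUG: effect 1.4 s, SD 2.0 s, margin 0.4 s. LAPAQ: effect 15 min, SD 30 min, margin 5 min. Correlation of the estimates +0.3. Stated power 86%.

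**Assumptions.** One-sided 2.5% for each test (no level is stated). Physical functioning is taken as baseline TUG; the PSC is another candidate, since section 8.a.II presents it as a measure of functional status, and the slope below would not apply to it. Covariate slope 0.5; assessor shift 0.25 SD.

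**1. The plan's own figures.** Generalised least squares with a random practice intercept, fixed period effects and empty implementation cells gives SE 0.213 SD, with 200 patients per condition (stated 0.21). With SEs of 0.42 s and 6.3 min, power is P(TUG superior, LAPAQ non-inferior) + P(LAPAQ superior, TUG non-inferior) − P(both superior) = 0.8237 + 0.6596 − 0.6252 = 0.858 (stated 86%). Both figures reproduce.

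**2. Form of the bias.** Let the outcome be y = θT + βx + time + practice + error, where T is condition and x the true baseline value. If the recorded baseline is x* = x + sT, then y = (θ − βs)T + βx* + time + practice + error. The estimate moves by −β × s. Under the split, the assessor indicator equals T in every measured cell, so neither time nor practice effects can separate the two. Simulated trials on this design with β = 0.5 and s = 0.5 s gave −0.251 s, against −0.25 s expected.

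**3. Size on TUG.** Shift 0.25 × 2.0 s = 0.5 s. Bias 0.5 × 0.5 s = 0.25 s, which is 0.25/0.4 = 63% of the margin and 0.25/1.4 = 18% of the planned effect. If physiotherapists record slower times than researchers, the bias favours Coach2Move; if faster, it goes against it.

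**4. Matching SE.** A slope of 0.5 also reduces residual variance: 0.213 × √(1 − 0.5²) = 0.213 × 0.866 ≈ 0.184 SD, or about 0.37 s. The LAPAQ SE is held at 6.3 min.

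**5. Effect on the combined objective (TUG SE 0.37 s).**

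| Truth | No bias | TUG bias 0.25 s |
|---|---|---|
| Both effects zero, bias favours Coach2Move: success | 1.6% | 3.6% |
| Effects 1.4 s and 15 min, bias against Coach2Move: power | 88% | 85% |

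The first row is the point where both effects are zero, not the maximum error of the rule.

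**6. Other baseline covariates.** EFIP and CIRS-G carry the same mechanism. With an assumed standardised slope of 0.1 to 0.3 and the same shift, the TUG bias is 0.1 × 0.25 × 2.0 = 0.05 s to 0.3 × 0.25 × 2.0 = 0.15 s.

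**7. QALYs.** By the trapezium rule, with T1 at three months as in section 8.c, baseline utility has weight 0.25/2 = 0.125 year. An assumed utility shift of 0.02 to 0.05 moves the QALY difference by 0.0025 to 0.006. The plan gives no target QALY difference to judge this against.

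**The case against.** The strongest reply is that one general sentence in section 4 is set against a specific procedure that three places describe consistently, and that the outcomes themselves are measured by researchers throughout. Therapists are trained in the use of measurement instruments. Section 7.b adds that "During the implementation period, the extensive intake will be carried out under supervision by a researcher of Radboudumc", and says of this "Furthermore, it is focussed to guarantee objectivity". TUG is routine in physiotherapy, and LAPAQ, EQ-5D and PSC rest on the patient's own answers. All of this lowers the risk. None of it measures agreement between the two kinds of assessor, and interviewing can still differ.

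It is also fair that every shift and slope above is assumed, and that a researcher-led baseline would repeat some of an intake that is itself part of Coach2Move, while section 4 wants to limit patient load. That is a real cost of the preferred remedy.

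Four stronger readings are tempting but not supported:

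- A reader might infer a second contradiction from section 10.b, "The researcher will subsequently make an appointment with the participant for the first assessment and will also deal with informed consent". It names who makes the appointment and handles consent, not who measures. Likewise "eligible patients are visited by the researcher within 1 week of registration" in section 7.b follows a sentence about the control period.
- A reader might infer a collapse in power. Slope 0.9 with shift 0.50 SD gives a bias of 0.90 s, and at the unadjusted SE of 0.42 s power would be 46%. But a slope of 0.9 shrinks the TUG SE to about 0.14–0.19 s, and power is then 81–87%, against 89% without bias. The same correction raises success at zero effects from 9.6% to 12.2%. The documents support neither that slope nor that shift.
- A reader might add a LAPAQ bias of some minutes. Baseline physical activity is not among the named covariates, so no particular figure follows.
- A reader might expect a model without the baseline measures to settle the matter. A true case-mix difference of 0.25 SD at slope 0.5 would bias that model by about 0.13 SD, as much as the assessor bias it avoids.

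**Conclusion.** The point holds in conditional form. The conflict between sections 4 and 8.c is in the text. Under the 8.c split, baseline assessor and condition are fully confounded within each practice, so any systematic shift in an adjusted baseline measure passes into the effect as slope times shift. That part is algebra. Whether a shift exists, how large it is and which way it runs cannot be learned from the documents. The 0.25 s case is an illustration resting on the assumptions listed in the working. It shows a bias that could matter next to a 0.4 s margin, with modest consequences for error and power. It does not show that the trial's result would be biased. The point is worth fixing because the remedy is cheap.

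**What to change.** Reconcile sections 4, 7.b and 8.c so that the baseline study measures use one script and one assessor type in both periods, as section 4 already implies. State which instrument represents physical functioning in section 9.b, and record the baseline assessor for each patient.

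If the split is kept:

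- At the supervised implementation intakes, where a researcher is already present, have researcher and physiotherapist both score the patient. Use these scores as agreement data only, since section 4 plans no trial measurements in that period.
- Keep the section 9.b model as primary. Prespecify a bias analysis that shifts the intervention-period baseline covariates, and baseline utility for QALYs, over the range those agreement data support.
- A model omitting the baseline measures may be reported as supportive, with the caveat that it cannot separate assessor shift from case mix.

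Cost: a little analysis work and text, and consent for research use of the paired scores. Scoring the same performance misses differences in how the test is instructed. If researchers do the baseline in the intervention period, that is about 60 minutes for each of about 200 patients (about 200 hours), with some repeat testing, unless section 4 means this is already resourced.

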9. STATISTICAL ANALYSIS

Descriptive statistics (mean, SD, proportions) will be used to report patient and PT(G) characteristics. Results on pre-structured questions on the interviews will be analysed using descriptive statistics (mean, SD, proportions).

The scores on the quality indicators of the patient files will be summarized using descriptive statistics. Descriptive summaries and charts will be produced presenting the quantitative results of the process analysis to help identify patterns of potential incomplete delivery.

a. Primary study parameter(s)

Cost-Effectiveness Analysis (CEA):

The Incremental cost-effectiveness ratio (ICER) “cost per Quality-Adjusted Life Year (QALY) gained” based on EQ-5D utilities will be computed and uncertainty will be determined using an appropriate method such as: the bootstrap method, Taylor expansion or the Fieller confidence interval method. A cost-effectiveness acceptability curve will be derived that is able to evaluate efficiency by using different thresholds (Willingness to Pay) for a QALY.

The cost analysis exists of two main parts. The direct costs of the regular physiotherapy and Coach2Move intervention will be determined on a per patient basis. Further, on patient level, volumes of care will be measured prospectively using medical records and cost questionnaires. Also travel time to the therapeutic sessions and related costs patients make will be considered.

The second part of the cost analysis consists of determining the cost prices for each volume of consumption in order to use these for multiplying the volumes registered for each participating patient. The Dutch manual for costing in evaluation analyses will be used [29]. For units of care/resources where no guideline or standard prices are available real cost prices will be determined. Research has shown that QALY's can be determined by applying a scoring method, such as developed by Versteegh and colleagues, on a meaningful health state classification measure, such as the EQ-5D. By means of the Dutch tariff, valuations can be determined for all possible health states as measured by the EQ-5D [27].

b. Secondary study parameter(s)

Quantitative Data Analysis

Data analysis to determine the overall effectiveness strategy subsequently involves comparison of the data points in the control section of the wedge with those in the intervention section. Because of the hierarchical design (patients nested within practices or within therapists), multilevel linear and logistic regression analysis will be used to compare the outcomes between treatment groups, with age, sex, comorbidity, frailty level and physical functioning at baseline at the patient level as covariates[13]. Time will be included as a fixed effect according to Donkers et al. [13]. In addition, subgroup analyses will be performed between PT and PTG levels.

c. Other study parameters

Qualitative Data Analysis

Interviews and focus group discussions will be elaborated verbatim (every word captured exactly, each final anonymised transcript will be added to the analysis). A structured thematic approach will be used to analyse the qualitative data.

The analysis will consist of five steps: 1) familiarization and initial coding line by line by two researchers; 2) developing a consolidated codebook; 3) coding and indexing all transcripts against the consolidated codebook, and discussion in the research group to focus on key findings for each study objective; 4) charting overall findings and look at any differences in patients, practices and context in dialogue with the project group and patient panel; 5) synthesis and drawing conclusions. In the analysis phase, descriptive summaries of interview data will be produced presenting the data per practice to help identify patterns.

Synthesizing quantitative and qualitative results:

An overall synthesis of the findings of the process evaluation study will take place to describe the context, the implementation of the intervention and the mechanisms of impact, with the aim of explicating the main trial findings and interrogating the intervention theory. Where data is available, we will test hypotheses based on qualitative analysis quantitatively. We will also, where appropriate, conduct the reverse operation and use quantitative data to focus qualitative analyses. Where data from different sources provide competing narratives or findings, we will make these explicit when reporting and provide a justification of our interpretation in such differences.

Budget Impact Analysis (BIA):

BIA will be performed according to the guidelines. Its purpose is to estimate the financial consequences of adoption and diffusion of standard use of the Coach2Move in the Netherlands. Several scenarios will be evaluated.

The aim is to assess these consequences in the medium-long term from the various budget holders' perspectives 1) wider societal perspective; 2) the more narrow perspective of the public purse; 3) the perspective of the health insurers; 4) the perspective of the health care provider.

Considering the budget impact of the new treatment mix, we will take into account market dynamics such as estimates of uptake of the Coach2Move induced treatment mix and substitution rates of usual care. For the BIA perspectives most of the cost are collected in the CEA and complemented with resources consumed not included in the CEA (like implementation costs). Both annual resource use (in terms of volumes consumed) and cost (volumes multiplied by prices) will be presented. With regard to prices and depending on the perspectives, several scenarios will be explored: charges, passenger rates (passanten tarieven), negotiated prices (if available) and real prices (CEA) based.

Effectiveness of the ultimate treatment mix will be accounted for as potential short-term savings in health care costs. The BIA will be assessed through modelling and analysed in a probabilistic way.

Deterministic uncertainty concerning BIA input such as the perspective, pricing parameters, time horizon, uptake, etc. will be dealt with by generating the budget impact as a series of scenario analyses covering a relevant range of costs.

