The TUG is a measurement for functional mobility. The TUG is a test commonly used in PT(G) care and allows international comparison. During the test, the patient is instructed to rise out of a chair, walk 4 meters, turn, walk back and sit down on the chair. This procedure is timed. The average time in seconds this takes is the score on this test. Due to limitations of place in housing of patients, the test we use is slightly modified: patients are required to walk 3 meter instead of the usual 4. Outcome is the amount of time in seconds it takes to complete this test. Gait speed has shown to be a reliable proxy indicator for the physical condition of older adults [26].

Another aspect of this study is the investigation of the potential efficiency of the Coach2Move strategy compared to usual care physiotherapy in frail elderly patients referred to physiotherapy by a physician or patients that enter the physiotherapy practice by direct access. The study perspective is societal. The informal caregiver is included in this economic evaluation. The economic evaluation is based on the general principles of a cost-utility analysis.

Primary outcome measures for the economic evaluation, considering the 12 months follow-up period are costs and direct and indirect and QALYs (EQ-5D, derived from the EuroQoL). The incremental cost-effectiveness ratio (ICER) “cost per QALY gained” will be computed and uncertainty surrounding this ICER will be determined using a non parametric bootstrap method. A cost-effectiveness acceptability curve will be derived that is able to evaluate efficiency by using different thresholds (Willingness to Pay) for a QALY gained. The impact of uncertainty surrounding deterministic parameters on the ICER will be explored using one-way sensitivity analyses on the range of extremes.

The cost analysis measures on patient level, volumes of care (consisting of the production factors: personnel, materials and capacity in a prospective way using patient/caregiver based diaries and therapist scoring sheets [CRFs]). Per arm full cost prices will be determined using

real costs of participating practices. If not available, standard cost prices according to the Dutch guidelines for costing research will be used.

Certain procedures standard cost prices are not available real cost prices will be determined using activity based costing. This approach applies to the health care production part of the economic evaluation.

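### The cost-per-QALY analysis states no period adjustment, practice effect or resampling unit, and nothing carries the time-adjusted multilevel estimates of section 9.b into the ICER

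*Combined protocol and SAP*

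**What the plan says.** The Summary (section 1) lists cost per QALY among the primary outcomes, and section 3 makes cost-effectiveness the main research question.

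- **Section 8.a.1** sets the horizon: the primary economic outcomes "considering the 12 months follow-up period are costs and direct and indirect and QALYs". It then says that "uncertainty surrounding this ICER will be determined using a non parametric bootstrap method", adds an acceptability curve, and explores deterministic parameters by "one-way sensitivity analyses on the range of extremes".
- **Section 9.a** repeats the ICER and the acceptability curve but leaves the method open: "uncertainty will be determined using an appropriate method such as: the bootstrap method, Taylor expansion or the Fieller confidence interval method".
- **Section 9.b**, under secondary parameters, sets multilevel linear and logistic models for comparing outcomes between treatment groups. They have patient covariates and time as a fixed effect, the latter by reference to a cited methods paper. The hierarchy is described as "patients nested within practices or within therapists".

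On prices, section 8.a.1 starts from the real costs of the practices and continues: "If not available, standard cost prices according to the Dutch guidelines for costing research will be used". It then says that where "standard cost prices are not available real cost prices will be determined using activity based costing". Section 9.a relies on the Dutch costing manual and says: "For units of care/resources where no guideline or standard prices are available real cost prices will be determined".

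**The concern.** In a stepped wedge, condition is tied to calendar time: control patients come early and intervention patients late. A comparison without period terms credits to Coach2Move any change over time in care use, case mix or utility. A variance that treats patients as independent also ignores clustering by practice.

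Sections 8.a.1 and 9.a define the ICER without naming a model for incremental cost or incremental QALY. They do not say whether the bootstrap resamples patients or practices. If Taylor expansion or Fieller were used, they do not say whether the variances and covariance of the two differences would allow for clustering. The adjustment that the design needs is written only in 9.b, with no sentence linking it to the ICER. The one-way sensitivity analyses in 8.a.1 do not fill the gap, because they concern deterministic parameters and not calendar time or clustering.

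At stake is the economic conclusion, and the cost inputs that the budget impact analysis takes from it. Trial success is declared on TUG and LAPAQ, which 9.b covers.

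**Working it through.** **Inputs from the documents.** Figure 1 in section 4 gives six 3-month periods and four groups of four practices, with one unmeasured implementation period per group. Section 6.d gives 5 patients per practice per measured period (400 in total) and an SE of 0.21 SD at ICC 0.10.

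**Assumed, because the documents do not give them.** The ICC for costs and QALYs is 0.01 to 0.10, recruitment is equal in every practice-period, and the SD is the same in both conditions. Results are in SD units.

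**1. The plan's own SE.** Take means of 5 patients per practice-period with a random practice intercept. Each mean has variance ICC + (1 − ICC)/5, and two means from one practice have covariance ICC. The variance of the effect is the treatment element of (X′V⁻¹X)⁻¹. At ICC 0.10:

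- with treatment and six period effects: SE 0.213, which matches the stated 0.21;
- with a practice effect but no period effects: SE 0.103;
- as a raw difference between conditions: SE 0.118.

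Only the period-adjusted model reproduces the plan's figure, so TUG and LAPAQ were sized with that adjustment.

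**2. Calendar separation.** Patients by entry period:

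| Period | 1 | 2 | 3 | 4 | 5 | 6 |
|---|---|---|---|---|---|---|
| Control | 80 | 60 | 40 | 20 | 0 | 0 |
| Intervention | 0 | 0 | 20 | 40 | 60 | 80 |

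Control mean = (80×1 + 60×2 + 40×3 + 20×4)/200 = 2.0. Intervention mean = (20×3 + 40×4 + 60×5 + 80×6)/200 = 5.0. The gap is 3 periods × 3 months = 9 months. The shorter practice list printed under the figure in section 6.d (4-3-3-3) gives 8.9 months.

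**3. Effect of a linear trend.** If 12-month costs or QALYs change by d per quarter of entry, a raw difference contains (5.0 − 2.0) × d = 3.0d. A practice effect without period terms does not remove it: the multiplier is 3.08, 3.26 and 3.34 at ICC 0.01, 0.05 and 0.10.

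**4. Effect of clustering alone.** A patient-level SE is √(2/200) = 0.100. The true variance of the raw difference is ICC × Σ[(n_int − n_ctl)/200]² + (1 − ICC) × 2/200. Per practice, n_int − n_ctl is 15, 5, −5 and −15 in groups 1 to 4. The sum is therefore 4 × (225 + 25 + 25 + 225)/40,000 = 0.05.

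| ICC | Variance | True SE | Coverage of nominal 95% interval, no trend |
|---|---|---|---|
| 0.01 | 0.0104 | 0.102 | 94.5% |
| 0.05 | 0.0120 | 0.110 | 92.6% |
| 0.10 | 0.0140 | 0.118 | 90.2% |

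**5. Both together, as an illustration.** Assume a drift of 0.1, 0.2 or 0.3 SD per year. Over 0.75 year the bias is 0.075, 0.15 or 0.225 SD. At ICC 0.10 and no true effect, a patient-level 5% test rejects 16%, 35% or 60% of the time, against 10% with no drift.

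**6. What adjustment costs.** At ICC 0, only periods 3 and 4 contain both conditions. Each has variance 1/40 + 1/20 = 0.075, so the pooled variance is 0.075/2 = 0.0375 and the SE is 0.194. At ICC 0.01, 0.05 and 0.10 the adjusted SE is 0.200, 0.211 and 0.213. Most of the widening from 0.100 is the price of period adjustment, not of clustering.

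**The case against.** **Section 9.b may already reach the components.** The Summary lists EQ-5D and health care utilization costs as secondary outcomes, and 9.b speaks of outcomes in general. Adjusted models of both may be intended, and a clustered bootstrap would fit the open wording of 9.a. This stands in part. Even so, separate models of EQ-5D and costs do not say how the ratio is formed, what is resampled, or which differences feed the acceptability curve.

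**A reader might infer that an unadjusted patient-level ICER is planned.** The documents do not support that. No sentence commits to it; the text only leaves it open.

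**A reader might infer that the ICER will be biased or its interval clearly too narrow.** That also goes too far. With no trend and an ICC of 0.01, coverage is close to nominal.

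**The separation in calendar time can be overstated.** By entry period, 140 + 140 = 280 of 400 patients have no concurrent comparator. But outcomes accrue over 12 months. With mid-quarter entry and full follow-up, 81% of person-time falls in quarters when both conditions are accruing. The two calendar distributions still overlap by only 35%, and their means stay 3 quarters apart. Section 4 fixes only a minimum of 25 patients per practice, so equal recruitment per period is the sample-size assumption, not a guarantee.

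**Two further readings should not be pressed.** Section 9.b does not simply leave time undefined; it delegates the definition to a cited paper. And the price text in 8.a.1 need not contradict itself: it can be read as a cascade from real practice costs to standard prices to activity-based costing. What differs is the starting point, real costs in 8.a.1 against guideline or standard prices in 9.a.

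**Conclusion.** The omission is clear and should be fixed. A listed primary outcome lacks the period adjustment and practice-level variance that the design requires and that the sample size calculation already uses for TUG and LAPAQ.

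Under Figure 1 with equal recruitment, an unadjusted ICER would take in about 3 times any linear quarterly trend. A patient-level interval would rest on an SE of 0.100 SD, where the period-adjusted SE is 0.200 to 0.213 SD over ICC 0.01 to 0.10.

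Confidence is high that the link is missing. The size of the harm is conditional, because it depends on a trend and an ICC that the documents do not supply. The coverage figures are for a single outcome, not for the ICER itself. The TUG/LAPAQ success rule and its power are not affected. The differing uncertainty methods in 8.a.1 and 9.a need reconciling; the order of price sources is a minor point.

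**What to change.** In section 9.a:

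- State that incremental costs and incremental QALYs come from models with fixed 3-month period effects, a random practice effect (the practice is the unit rolled out), the patient covariates of 9.b and, for QALYs, baseline EQ-5D utility.
- Derive the ICER and the acceptability curve from these adjusted differences.
- Name one joint cost-QALY uncertainty method that respects clustering by practice and is valid for 16 practices. Examples are the joint model covariance, or a bootstrap of whole practices within rollout groups with a small-sample correction. The correction matters because resampling four practices per group in effect divides by 4 rather than 3, which understates between-practice variance by roughly a quarter.

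Make section 8.a.1 name the same method, and give one order of price sources in both sections.

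The cost is SAP wording and some programming, with no new data. The economic interval will be wider, with an SE of about 0.20 to 0.21 SD instead of 0.10 SD, so the ICER will be less precise than an unadjusted analysis would suggest.
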